**3. PMS DESIGN OVERVIEW (AMENDED: 14 MAY 2018)**

Sequential Allocation of Subject Numbers					
Cervarix (N ~ 600)					
Vaccination Dose 1	Follow-up 30-day follow-up after Dose 1	Vaccination Dose 2	Follow-up 30-day follow-up after Dose 2	Vaccination Dose 3	Follow-up 30-day follow-up after Dose 3

N: Number of subjects planned to be enrolled

PMS conclusion will depend on the concluding visit of the subject in the PMS.

Definition of Conclusion of PMS for a subject: Subjects who have completed 30-day follow-up after at least one dose, regardless of the number of doses, are considered to have completed the PMS.

Note: Eligible subjects can be enrolled at any stage in the PMS regardless of Cervarix dose(s) received previously.

Follow-up for AEs will continue for 30 days after receiving each vaccine dose(s) in the PMS. Follow-up of SAEs will continue from the date of Visit 1 until 30 days after the last dose received in the PMS. Cervarix will be vaccinated according to local practice

Protocol waivers or exemptions are not allowed unless necessary for the management of immediate safety concerns. Therefore, adherence to the study design requirements, including those specified in the outline of study procedures (Section 8), are essential and required for study conduct. ***This PMS will be conducted by a continuous surveillance method.***

- PMS design: A prospective, observational, non-comparative, multi-centre PMS in Korea.
- Study population: 9-25 years old males and females.
- Vaccination schedule: Cervarix will be administered as per the local PI in Korea.

The recommended schedule is as follows:

- Vaccination: The 9-25 years old subjects should be administered Cervarix with 3 doses (**0.5mL each**), 0, 1, and 6 months schedule. The 9-14 years old subjects can be vaccinated with 2 doses, 0 and 6-12 months schedule. ***In the 2-dose schedule, if the second dose is administered before 5 months after the first dose, the third dose vaccination is required. In the 3 doses schedule, if the vaccination schedule requires flexibility, the second dose can be administered between 1 and 2.5 months and the third dose can be administered between 5 and 12 months after the first dose.***

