### 11.3.2. Total Safety cohort

Safety analysis based on all vaccination groups will include all subjects who were vaccinated per product information and have completed 30-day follow-up after at least one dose, regardless of the number of dose.

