4.1 Safety Analysis Set (Total Safety cohort)

In standard for re-examination of new drugs, etc.(2012), the point to reported is defined as follow. (Chapter II, no 3).

2) Patient Population for Surveillance

A) Patients planned to receive a drug under surveillance by investigator's medical judgment shall be defined as a subject.

- B) Subject who do not use within approved range shall not be included in the safety analysis set in principal.
- ※ However, if data of subject whose use is beyond approved range is collected, perform analysis as a separate item.
- C) How to actually select subjects shall be described in detail.

The definition of the safety analysis set to this study is as follows.

Subjects who have been completed 30-days follow-up after at least once vaccinated Cervarix, will be included in the safety analysis set.

The below cases shall be excluded from the safety analysis set in the following order.

- (1) Subject who consented prior to the site initiation date
- (2) Subject who completed administration of Cervarix prior to the site initiation date
- (3) Subject who completed administration of Cervarix prior to the consent date
- (4) Subject who did not receive Cervarix
- (5) Follow-up failure: Subject for whom adverse event status (Adverse events status is unknown or missing) could not be established
- (6) Subject who has been violated the inclusion/exclusion criteria

[Inclusion criteria]

- Subject or/and subjects whose parent(s)/Legally Acceptable Representative(s) [LAR(s)], in the opinion of the investigator, can and will comply with the requirements of the protocol (e.g., complete the diary cards, return for follow-up visits).
- Korean male or female subjects aged 9-25 years who are eligible for the series of Cervarix according to the locally approved PI.
- Written informed consent obtained from the subject/from the parent(s)/LAR of the subject.

[Exclusion criteria]

- At the time of PMS entry, the contraindications and precautions of use indicated in the locally approved PI. PI should be checked and the subject must not be included in the PMS if there is any contraindication.
- Subjects who had previous administration of a HPV vaccine other than Cervarix will not be enrolled into the study.
- Subjects who are not eligible for vaccination with Cervarix according to the medical judgement of physician

- Child in care.
- (7) Subject who has been violated the dosage
- [Dosage]
- Receive 0.5mL dose by intramuscular injection

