 - The 9-14 years old subjects can be vaccinated with 2 doses, 0 and 6-12 months schedule or with 3 doses, 0, 1 and 6 months schedule.
 - The 15-25 years old subjects should be vaccinated with 3 doses (0.5 mL each), 0, 1 and 6 months schedule.
 - In the 2-dose schedule, if the second dose is administered before 5 months after the first dose, the third dose vaccination is required. In the 3 doses schedule, if the vaccination schedule requires flexibility, the second dose can be administered between 1 and 2.5 months and the third dose can be administered between 5 and 12 months after the first dose.

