6.7 Cervarix Vaccination Information

The following continuous data will be summarized with descriptive statistics.

- Pre-vaccination body temperature

The following categorical data will be summarized with descriptive statistics.

- Vaccination history of prior Cervarix ^a
- Dose number of Vaccination history of prior Cervarix
- Total number of Cervarix vaccination in the PMS
- Order of Cervarix vaccination

Pre-vaccination body temperature will be presented per each visit.

^a vaccination history of prior Cervarix: In case of that has/have received one or two dose(s) of Cervarix before the enrollment

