6.8.3 Incidence Proportion by Baseline Background Factor

For all adverse events, the number of subjects to whom adverse event occurred and the number of adverse events will be presented per each categorical baseline background factor and special study group described in section 6.2 ~ 6.7. Also, the incidence proportion of adverse event and its 95% confidence interval will be presented.

The incidence proportion of adverse event and its 95% confidence interval will be presented and analyzed using Chi-square test or Fisher's exact test per each baseline background factor. However, some continuous variables not categorized such as height, weight will be excluded from analysis.

In the re-examination, multiple logistic regression will be performed to identify the factors that affect the incidence proportion by baseline background factor and special study group. All of factors that are statistically significant (p-value < 0.05) will be included in the model. However, as considering the structure and characteristics of the collected data, the factors used for the actual analysis can be added or subtracted.

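### SAP 6.8.3 tests an any-AE proportion that accumulates over one to three 30-day windows, so the number of PMS doses can look like a risk factor through observation time alone

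*SAP*

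**What the plan says.** Four parts of the plan combine.

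- **Observation.** Protocol section 3 states "Follow-up for AEs will continue for 30 days after receiving each vaccine dose(s) in the PMS". It also states "Eligible subjects can be enrolled at any stage in the PMS regardless of Cervarix dose(s) received previously". A subject's AE observation is therefore 30 days times the number of doses received inside the PMS.
- **Analysis set.** Protocol 11.3.2 takes subjects who "have completed 30-day follow-up after at least one dose, regardless of the number of dose". SAP 4.1 agrees: "Subjects who have been completed 30-days follow-up after at least once vaccinated Cervarix, will be included in the safety analysis set". Subjects with one, two and three windows all belong.
- **Outcome and denominator.** SAP 6.8.3 says: "For all adverse events, the number of subjects to whom adverse event occurred and the number of adverse events will be presented". It names no window, dose restriction or person-time. SAP 5.5 sets the denominator as subjects in each category.
- **Factors and tests.** The results are given "per each categorical baseline background factor and special study group described in section 6.2 ~ 6.7", each factor being tested by chi-square or Fisher's exact test at two-sided 0.05. SAP 6.7 lists "Total number of Cervarix vaccination in the PMS", which SAP 7.2 splits into one, two and three doses, and also prior Cervarix (yes or no). SAP 7.2 splits age into 9 to 14 and 15 to 25. On schedule, SAP 4.1 states "The 15-25 years old subjects should be vaccinated with 3 doses (0.5 mL each), 0, 1 and 6 months schedule", while ages 9 to 14 may follow two or three doses.

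Factors with p<0.05 go into a multiple logistic regression at the re-examination, and factors may be added or dropped in light of the data. Under SAP 5.5 the regression is not run if two or fewer factors are significant.

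**The concern.** A subject observed for 90 days has more opportunity to report at least one event than a subject observed for 30. If both count once in a per-subject proportion, a comparison across number of doses mixes risk with observation time.

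The total number of PMS doses is the clearest case, because it equals the number of windows. It is also not a baseline factor: under protocol 7.2 a contraindicating event ends further dosing, so the outcome can change the factor. Prior Cervarix limits how many windows remain. Concomitant medication and vaccination (SAP 6.5 and 6.6) are counted within 30 days after Cervarix vaccination with no single dose named, so more doses give more chance of a yes. Age may track the number of windows through the schedule.

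At stake is the re-examination report. It could tell the regulator that a factor affects AE incidence when the subjects differ only in how long they were watched.

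**Working it through.** **Plan's own figure.** Protocol Table 6 gives exact 95% intervals for 600 subjects. Clopper-Pearson limits reproduce all eight rows to one decimal (for example 5%: 3.40 to 7.06, stated 3.4 to 7.1). That table concerns one overall proportion and is not in question. The plan gives no figure for the factor comparisons.

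**Assumptions, none stated in the documents.** Per-dose AE risk p, identical at every dose and in every subject type: 2% to 20%, within Table 6's 1% to 20% range. Within-subject correlation ρ: 0 or 0.3. Group sizes as shown.

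**Step 1: proportion with any AE over k windows.** Independent doses: 1 − (1 − p)^k. Correlated doses (beta-binomial): 1 − ∏ (b + i)/(a + b + i) for i = 0 to k − 1, with a = p(1 − ρ)/ρ and b = (1 − p)(1 − ρ)/ρ.

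At p = 20%, independent: 20.0%, 1 − 0.8² = 36.0%, 1 − 0.8³ = 48.8%. With ρ = 0.3: 20.0%, 31.2%, 38.6%. At p = 5%: 5.0%, 9.8%, 14.3% and 5.0%, 8.3%, 10.8%.

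**Step 2: chance of p<0.05 with no true dose effect.** Two-sided two-proportion test, normal approximation: Φ[(d − 1.96·s0)/s1], with d the difference, s0 the pooled and s1 the unpooled standard error. Example, p = 5%, independent, 150 one-window versus 300 three-window subjects: d = 0.0926, s0 = 0.0315, s1 = 0.0269, so Φ(1.15) = 0.87.

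| Per-dose risk | 1 v 3 windows, 150/300: ρ=0 | ρ=0.3 | 2 v 3 windows, 300/300: ρ=0 | ρ=0.3 |
|---|---|---|---|---|
| 2% | 0.45 | 0.23 | 0.19 | 0.10 |
| 5% | 0.87 | 0.54 | 0.40 | 0.18 |
| 10% | 0.99 | 0.84 | 0.65 | 0.29 |
| 20% | 1.00 | 0.99 | 0.89 | 0.48 |

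The nominal value is 0.05 throughout. Stronger clustering weakens the effect without removing it: at ρ = 0.6 and p = 20%, two versus three windows gives 0.17.

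**Step 3: age group.** The two-versus-three columns apply to age only if every subject aged 9 to 14 has two windows and every subject aged 15 to 25 has three. With mixed windows at p = 20%, independent, 300 per group:

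- Younger 25/50/25% and older 25/25/50% in one/two/three windows: 0.25×20 + 0.50×36 + 0.25×48.8 = 35.2% against 0.25×20 + 0.25×36 + 0.50×48.8 = 38.4%. Chance of p<0.05: 0.13 (0.08 at ρ = 0.3).
- Younger 10/60/30% and older 30/30/40%: 38.2% against 36.3%. The direction reverses.

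**Step 4: one window per subject.** Simulating 4,000 trials at each risk with 200 subjects per dose-number group and independent windows, the three-group chi-square test on the cumulative outcome rejected in 82%, 99% and 100% of trials at p = 5%, 10% and 20%. With one common window it rejected in 5.1%, 5.4% and 4.8%.

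**The case against.** The best defence is that this is a descriptive surveillance. Its objective is frequency and intensity of events, protocol 11.4.2 says interim results will not affect conduct, and SAP 6.8.1 separately analyses the 30 days after each dose. A reader could see equal by-dose rates there. That limits the harm, but nothing carries the by-dose analysis into the 6.8.3 tests or the model, and the SAP does attach significance tests to these comparisons.

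A second defence is that the regression would adjust. In part it might: if number of doses enters, it would partly adjust age and prior Cervarix. But it would then itself be reported as a factor affecting incidence. With two or fewer significant factors no model is run and the unadjusted tests stand alone. The freedom to add or drop factors is not a rule for equalising observation time.

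A third is that the number of doses is not a baseline factor and so might be left out. SAP 6.8.3 sends the reader to all categorical factors of 6.2 to 6.7, excludes only uncategorised continuous variables, and SAP 7.2 gives this item categories.

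Two stronger readings are tempting and not supported. A reader might infer that older subjects will show more events. Ages 9 to 14 may take two or three doses and either age group may enter at any dose, so the age contrast can be near nominal or reversed. A reader might also infer that unequal SAE follow-up, which runs continuously to 30 days after the last PMS dose, distorts separate SAE comparisons. SAP 6.8.3 specifies no SAE-specific factor test.

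Stopping of doses after an event pushes the other way, towards more events among subjects with fewer doses. It may offset part of the effect in unknown measure, and it is a further reason not to test this variable.

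**Conclusion.** The point holds for the number of PMS doses, by construction, and for prior Cervarix and the concomitant factors to the extent that they go with fewer or more windows. For age group it is a possibility whose size and direction depend on schedule and entry mix; the two-versus-three figures are the extreme case.

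The false-positive chances rest on assumed risks, group sizes and correlation. Across the range shown, every contrast of uniformly one versus three or two versus three windows exceeds 0.05, but at 2% risk the excess is much smaller than at 20%. The overall AE proportion and the by-dose tables are not affected. The change should be made, but it does not threaten the main safety description.

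**What to change.** In SAP 6.8.3:

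1. Define the tested outcome as any AE on Day 1 to Day 30 after the first Cervarix dose received in the PMS, for all factor tests and the logistic model.
2. For these tests, define concomitant medication and vaccination over the same window.
3. Show the total number of PMS doses descriptively, without a test and outside the model.
4. Dose order may be tested as the order of that first PMS dose. It also determines prior Cervarix (yes or no), so the two should not enter the model together.
5. Keep the all-dose proportion and the by-dose tables as the descriptive summary.

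The cost is SAP wording and derived flags from dates already collected. The downside is that events after later doses do not enter the factor tests. If the sponsor wants to keep them, a per-dose model allowing for repeated doses within subject, or an offset for number of windows, would also serve, at the price of a more complex analysis.

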6.8.4 Adverse Events for Subjects in Non-Safety Analysis Set

According to chapter 2, Item 3 of the Ministry of Food & Drug Safety (MFDS) guideline, the incidence proportion of adverse event of subjects whose use is beyond approved range will be presented. However, 'subjects who have not taken this study drug' and 'follow-up failure' will be excluded from this analysis because their safety assessment is not available.

Below items of adverse event in accordance with SOC and PT or IT will be presented for the number of subjects, incidence proportion, its 95% confidence interval using exact method and the number of adverse events.

- Adverse event · Adverse drug reaction
- Serious adverse event · Serious adverse drug reaction
- Unexpected adverse event · Unexpected adverse drug reaction
- Unexpected serious adverse event · Unexpected serious adverse drug reaction
- Unexpected non-serious adverse event · Unexpected non-serious adverse drug reaction

Detailed adverse events will be listed by subjects for the following items

- Serious adverse event
- Unexpected adverse event
- Unexpected serious adverse event
- Adverse event of subject with liver disease
- Adverse event of subject with renal disease
- Adverse event leading to withdrawal

6.8.5 Other Safety Analyses

Preferred terms of serious adverse event · serious adverse drug reaction, unexpected adverse event · unexpected adverse drug reaction will be presented respectively according to the proportion category of AEs in the local PI.

6.9 Effectiveness Evaluation

Not Applicable

7. Derivation and Categorization for Variable

7.1 Derivation

The calculation formulas are as follow. However, the following may be considered.

- If statistical analysis requires additional calculation formula, SAP may not be revised unless it relates to key variable, but the calculation formula will be specified in TLFs.

Age (years)

- In case of month of Informed Consent \geq Month of Birth:

$$\text{Age} = (\text{Year of Informed Consent}) - (\text{Year of Birth})$$

- In case of month of Informed Consent $<$ Month of Birth:

$$\text{Age} = (\text{Year of Informed Consent}) - (\text{Year of Birth}) - 1$$

- In case of missing month:

$$\text{Age} = (\text{Year of Informed Consent}) - (\text{Year of Birth})$$

BMI (kg/m²)

- Weight(kg) / Height²(m²)

7.2 Categorization

Categories for each item are as follows.

However, the following defined category for continuous variable can be changed according to the distribution of actual collected data.

| Item | Category |
|---------------------|--------------------------------|
| • Pediatric subject | < 18 years, \geq 18 years |
| • Geriatric subject | < 65 years, \geq 65 years |
| • Pregnant subject | Yes, No, NA |
| • Liver disease | Yes, No |
| • Renal disease | Yes, No |

| Item | Category |
|--|---|
| • Age | 9 ~ 14 years, 15 ~ 25 years |
| • Gender | Male, Female |
| • Ethnicity | Korean, Non-Korean |
| • Past medical history | Yes, No |
| • Current medical history | Yes, No |
| • Prior medication | Yes, No |
| • Concomitant medication | Yes, No |
| • Prior vaccination | Yes, No |
| • Concomitant vaccination | Yes, No |
| • Vaccination history of prior Cervarix | Yes, No |
| • Dose number of Vaccination history of prior Cervarix | Dose 1, Dose 1 and Dose 2 |
| • Total number of Cervarix vaccination in the PMS | One dose, Two doses, Three doses |
| • Order of Cervarix vaccination | 1st dose, 2nd dose, 3rd dose |
| • Site | Non-Administration site, Administration site |
| • Outcome | Recovered, Not recovered, Recovering, Resolved with sequelae, Fatal (SAEs only), Unknown |
| • Maximum intensity | Mild, Moderate, Severe |
| • Relate to Cervarix | Certain, Probable / Likely, Possible, Unlikely, |

| Item | Category |
|--------------------------|---|
| | Conditional / Unclassified, Unassessable / Unclassifiable |
| • Medical attended visit | None, Hospitalization, Emergency Room, Medical Personnel |

References

The minister of Food and Drug Safety. Practical guideline for re-examination of new drugs. 2012

GlaxoSmithKline (GSK). A prospective, observational, multi-centre, post-marketing surveillance (PMS) to monitor the safety of GlaxoSmithKline (GSK) Biologicals' human papillomavirus (HPV)-16/18 vaccine, Cervarix when administered to 9-25 years old subjects according to the approved Prescribing Information in Korea.

Appendix

Mock up TLFs
